- Total number of subjects to be enrolled at this site (enter -1 for chart reviews, banking, registries):
 34
- 2. Describe and explain the study design:

The proposed study will be conducted as a single-center prospective, cross-over, placebo-controlled clinical trial at the University of Pittsburgh Medical Center (UPMC).

3. Describe the primary and secondary study endpoints:

Urine volume (collected each visit over 6-hour time frame) Electrolytes: sodium, potassium, chloride Urine osmolarity Urine creatinine

4. Provide a description of the following study timelines:

Duration of an individual subject's active participation:

The individual's active participation will involve three separate sessions, each lasting approximately 6 hours (total of 18 hours for each participant). Study visits will be completed within a three-to-four month period.

Duration anticipated to enroll all subjects:

Approximately 9 months

Estimated date for the investigator to complete this study (complete primary analyses):

4/1/2024

5. List the inclusion criteria:

- Male or female, >18 to 45 years of age
- Freely given written consent
- Non-tobacco users
- Negative pregnancy test in women of childbearing potential
- BMI < 35 kg/m2
- GFR > 60 ml/min
- No known underlying medical condition
- Willing to refrain from EtOH for 24h prior to test day
- Willing to refrain from strenuous exercise for 24 h prior to each test day
- Acceptable to have one 8oz cup of coffee/liquid on the morning of the test, but must be consistent each visit
- · Without active infection of any kind
- Engaged in exercise three or more hours per week

6. List the exclusion criteria:

- Abnormal creatinine (Cr > 1.2).
- Proteinuria / hematuria / glucosuria based on urine dipstick.
- Diagnosed medical condition that would impede results (CHF, HTN, CAD, CKD,
- history of electrolyte abnormality).
- Pregnancy
- Use of diuretics within past 2 weeks
- Obesity (BMI > 35)
- Active infection based on symptoms (bacterial or viral)

• Hemodynamic abnormality at screening visit: Blood pressure less than 100/60 or greater than 140/90.

7. Will children or any gender, racial or ethnic subgroups be explicitly excluded from participation?

• Yes O No

* Identify the subgroups and provide a justification:

Children will be excluded from participation since the study is looking at the hydration status of active adults.

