8. Describe the power analysis used and cite your method of statistical analysis. If a power analysis is not possible, thoroughly justify the sample size required for the study, including appropriate literature citation (alternatively provide page reference in attached protocol):

The data will be presented as mean \pm SD, analyzed using the conditions x time analysis of variance (ANOVA), while BHI will be analyzed using a one-way ANOVA. Tukey post-hoc testing and contrast analysis can be used as appropriate. Statistical significance was set at p \leq 0.05.

We aim to have 30 subjects complete the study. This is a pilot study to inform a future large-scale trial with appropriate power calculation.

Research Activities

 * Provide a detailed description of all research activities (including screening and follow-up procedures) that will be performed for the purpose of this research study. This description of activities should be complete and of sufficient detail to permit an assessment of associated risks.

Prior to initiation of the study, subjects will complete a brief phone screen to assess basic eligibility and will be asked to fast. The screening visit will consist of informed consent, health history, and discussing eligibility requirements for each study visit, including (1) refrain from vigorous exercise for 24 hrs prior, (2) fast overnight for at least 10 hrs, (3) empty bowel and bladder upon waking up, (4) can consume one 8oz cup of coffee or tea. For female subjects, this will also include their last date for menstruation and/or birth control method to take into consideration the effects of ovulation on water retention.

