Prior to initiation of test blood pressure and heart rate will be measured. Urine will be collected and discarded.

At time 0, the participant will begin to drink fluid (drinking 6.25% of their total amount every 15 min). Urine will be collected at 60, 120, 240, and 360 min. Bioimpedence will be measured after each urine collection. Collect urine for a total of 6 hours. VISIT 2—WATER CONTROL: Participants will ingest 1 L of water at a rate of 6.25% of the calculated amount of water every 15 min for 4 hours.

Prior to initiation of test blood pressure and heart rate will be measured. Urine will be collected and discarded.

At time 0, the participant will begin to drink fluid (drinking 6.25% of their total calculated amount every 15 min). Urine will be collected at 60, 120, 240, and 360 min. Bioimpedence will be measured after each urine collection. Collect urine for a total of 6 hours.

VISIT 3—NUUN INTERVENTION: The goal is to give a one-time dose of 2 tablets of Nuun Sport (600mg Na+) at the start of the trial, diluted in 1L water to be consumed within 30 min (similar to prior published data, Pence 2020).

Prior to initiation of test blood pressure and heart rate will be measured. Urine will be collected and discarded.

At time 0, the participant will consume the beverage over 30 min. Urine will be collected at 60, 120, 240, and 360. Bioimpedence will be measured after each urine collection. Collect urine for a total of 6 hours. Patients will be compensated \$300 after completion of three visits.

Buoy is an all-natural, organic, FDA compliant dietary electrolyte supplement that can be dissolved in 8-12oz water (or other liquid) and provide electrolytes in servings of 1/3 teaspoon. Nuun are electrolyte tablets that are added to water to improve fluid balance and beverage hydration index (BHI) in healthy individuals (Pence, 2020). Nuun tablets contain a mix of electrolytes, including calcium, magnesium (as an oxide), chloride, sodium, and potassium. The recommended use of Nuun is one tablet dissolved in water, administered once daily.

The PI and study team will be performing the research procedures. A phlebotomist will be used to complete the blood draws.

Following each study visit, a boxed lunch will be offered to each participant. This lunch will be Jimmy John's (or a similar sandwich shop). Each participant will be asked about preferences and food allergies during the screening process so provide an appropriate option for participants involved.

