All data will be stored with a unique ID and will be kept on a secure server or in locked filing cabinet in a secure office.

Subjects will be encouraged to bring a snack with them to eat after the completion of fasting.

3. Financial risks - will the subject or insurer be charged for any research required procedures?

O Yes No

4. Describe the steps that will be taken to protect subjects' privacy:

All research interventions will be conducted in a private exam room. Collection of sensitive information about subjects is limited to the amount necessary to achieve the aims of the study.

5. What steps will be taken in the event that a clinically significant, unexpected disease or condition is identified during the conduct of the study:

Should a clinically significant, unexpected disease or condition be identified during the conduct of the study, the patient's primary medical team will be immediately notified of the unexpected, clinically significant condition. The patient's clinically significant medical condition will be managed accordingly. If any of the clinically significant medical conditions is related to the study, then the patient's participation in the study will be re-evaluated, with the possibility of the patient being withdrawn from the study if it leads to the resolution of the clinically significant medical condition.

6. Describe the potential benefit that individual subjects may experience from taking part in the research or indicate if there is no direct benefit. Do not include benefits to society or others:

Participation in the research does not offer direct benefit to the research subjects.

7. Do you anticipate any circumstances under which subjects might be withdrawn from the research without their consent?

O Yes No

8. Describe procedures that will be followed when subjects withdraw from the research, including partial withdrawal from procedures with continued data collection and data already collected:

Any identifiable research or medical information recorded for, or resulting from, participation in the research study prior to the date of withdrawal may continue to be used and disclosed by the investigator for the purposes of research. Data will continue to be stored on secure servers and de-identified prior to analysis.

Conflict of Interest

Institutional Financial Interests

1. * To the best of your knowledge, has the University of Pittsburgh optioned or licensed technology that will be tested or evaluated in this research?

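### The conditions-by-time ANOVA has no participant term, analysis set or missing-data rule; as usually run, it would drop complete Buoy-water pairs when only the Nuun visit is missed

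*Combined protocol and SAP*

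**What the plan says.** Study Design item 1 sets the "Total number of subjects to be enrolled at this site" at 34. Item 8 adds "We aim to have 30 subjects complete the study" and calls the trial a pilot: "This is a pilot study to inform a future large-scale trial with appropriate power calculation". No effect size, SD or dropout rate is given.

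The analysis is also in item 8. Data are to be "analyzed using the conditions x time analysis of variance (ANOVA"), "while BHI will be analyzed using a one-way ANOVA", with Tukey tests and contrasts as options and a threshold of 0.05. The item does not mention repeated measures, a participant effect, an analysis set, or what happens when a visit or reading is missing.

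Research Activities item 1 has each participant take all three conditions: Buoy at Visit 1, water at Visit 2 and Nuun at Visit 3 ("The goal is to give a one-time dose of 2 tablets of Nuun Sport"). Urine is collected at 60, 120, 240 and 360 minutes of each visit, and bioimpedance follows each collection. Volume is recorded on site and only part of each collection goes to the laboratory.

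Study Aims 1 and 2 concern total urine volume and total body fluid under Buoy. Neither names a comparator, but water is labelled the control and Nuun appears only in Aim 3. Risk and Benefits item 8 says information recorded "prior to the date of withdrawal may continue to be used and disclosed by the investigator for the purposes of research".

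**The concern.** The value of a crossover lies in comparing each person with themselves. For Aims 1 and 2 the natural comparison is Buoy against water, and both visits come before Nuun in the written order. A person who stops after Visit 2 has supplied everything that comparison needs, and the withdrawal section lets those data be used.

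Item 8 gives no route for using them. A conditions-by-time ANOVA can be run in two common ways. The repeated-measures form respects the pairing but needs every cell from every person. The ordinary factorial form keeps incomplete people but treats readings from one person as independent, which gives up the benefit of the crossover. Neither is satisfactory, and the choice is left until after the data are seen. At stake are a small loss of precision on Aims 1 and 2, a possibly larger loss on the serial laboratory outcomes, and an analysis set that is not fixed in advance.

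**Working it through.** **Inputs.** From the protocol: 34 enrolled (Study Design item 1); 30 completers and threshold 0.05 (item 8); 3 conditions and 4 timed collections (Research Activities item 1). Assumed here, because the documents do not say: two-sided testing, a true Buoy-water difference of 0.5 SD of the paired differences, and 1%, 2% or 5% independent loss per laboratory reading.

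**1. The plan's own figures.** The gap from 34 to 30 implies attrition of 4/34 = 11.8%. It would also fit a 10% allowance (30/0.90 = 33.3, rounded up to 34), but no rate is stated. The 30 itself cannot be reproduced, since no effect size or SD is given.

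**2. Cells required.** 3 conditions x 4 times = 12 cells per person, of which 8 belong to Buoy and water.

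**3. What each form of the model does.** Take 34 simulated people, 4 without a Nuun visit: 30 x 12 + 4 x 8 = 392 rows. A standard repeated-measures ANOVA routine rejected these data as unbalanced and ran only on the 30 complete people. An ordinary factorial ANOVA, an ANOVA with participant as a factor, and a mixed model each used all 392 rows.

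**4. Missed Nuun visit.** If all four losses fall after Visit 2, 34 Buoy-water pairs exist and the complete-case analysis uses 30. The 95% half-width, in SDs of the paired difference, is t(0.975, n-1)/sqrt(n). Power is from the noncentral t distribution with n-1 degrees of freedom and noncentrality 0.5 x sqrt(n).

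| Pairs | Half-width | Difference detectable with 80% power | Power at 0.5 SD |
|---|---|---|---|
| 30 | 0.373 | 0.529 | 75.4% |
| 32 | 0.361 | 0.511 | 78.2% |
| 34 | 0.349 | 0.495 | 80.8% |

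The half-width ratio, 34 against 30, is 0.934, so the interval is about 7% narrower. The standard error alone falls by 1 - sqrt(30/34) = 6.1%. If all four losses fall before Visit 2 is completed, only 30 pairs exist and the gain is zero.

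**5. Lost laboratory readings.** Among 30 people who attend all visits, the expected number with all 12 readings is 30 x (1 - p)^12:

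- p = 1%: 30 x 0.99^12 = 26.6
- p = 2%: 30 x 0.98^12 = 23.5
- p = 5%: 30 x 0.95^12 = 16.2

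This applies only to urine electrolytes, osmolarity and creatinine. Aim 1 uses one 6-hour total per visit, built from volumes recorded on site, so a lost laboratory portion leaves it intact. Aim 2 rests on bioimpedance, which does not use the sample.

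**The case against.** The strongest reply is that the plan contains no deletion rule. Item 8 does not say repeated measures, listwise deletion or completers only. Some ANOVA fits keep incomplete people, and the optional contrasts could be run on available Buoy-water pairs. The sentence about 30 people is a completion target, not an analysis set. All of this stands. A reader might infer that the plan discards people who miss Nuun, or that its method cannot use their data; the documents do not support that. The loss is a risk from a model left unspecified. The reply does not remove the point, because the plan does not commit to any fit that both respects the pairing and keeps these people.

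A reader might also infer that missing samples bias Aim 1, because samples are likelier to be missing when output is low, the direction that Aim 1 counts as success. That does not follow either. A collection with no urine is a volume of 0 mL, and a lost laboratory portion does not erase a recorded volume. The counts in step 5 therefore say nothing about Aims 1 and 2.

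Finally, the gain may be smaller than the upper bound. Consent precedes the screening tests, so part of the gap from 34 to 30 could be screen failures or early dropout. Payment only after all three visits discourages stopping after Visit 2. Loss of readings clustered within a few people would leave more complete cases than step 5 shows. These points stand, and for that reason the size is given as a range that starts at zero.

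**Conclusion.** The concern holds as one about an unspecified model for which a better choice is available at almost no cost. As usually run, the named ANOVA would drop people who have both visits needed for the apparent Aim 1 and 2 comparison; run as an ordinary ANOVA, it would ignore the crossover.

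For Aims 1 and 2 the gain lies between nothing and four extra pairs: an interval 0 to about 7% narrower, and power at an assumed 0.5 SD difference of 75% rising to at most 81%. The upper end requires that all four losses in the plan's own gap occur between Visits 2 and 3. It also takes water as the comparator, which the aims do not state.

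For the serial laboratory outcomes, an assumed independent loss of 1% to 5% per reading would leave about 27 to 16 of 30 people with complete profiles. The documents give no loss rate, so this shows sensitivity and is not a forecast.

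**What to change.** State in Study Design item 8:

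- Serial outcomes are analysed with a likelihood-based mixed model on all available readings, with participant as a random effect and condition, time and their interaction as fixed effects.
- The Buoy-water contrast is estimated from everyone with both visits, whether or not the Nuun visit took place.
- Aim 1 is analysed as the 6-hour total volume, with a collection that yields no urine entered as 0 mL.
- The analysis of participants with all three visits is reported as a sensitivity analysis.

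The cost is analysis wording only, with no new data, visits or participants. The downside is that the number analysed differs slightly between aims and outcomes, so each result should carry its own count. The model uses incomplete profiles but does not by itself correct for readings that are missing because of their unseen values; reporting the number missing by condition and time would let a reader judge that.

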Prior to all research visits (screening, visits 1, 2, and 3), participants must refrain from vigorous exercise (exercises that results in a high heart rate and rapid breathing) within 24 hours of study visit. Participants will fast (food) overnight for 10h prior to initiation of test. Upon waking they are asked to empty their bowel and bladder. They can consume one 8oz cup of coffee or tea (plain with no sugar or additives) to reduce caffeine headaches. They will present at 7-8am, which will be pre-specified. Prior to emptying their bladder, a blood draw of up to 1 ml will be drawn by a trained phlebotomist for the i-STAT testing, which will be used to measure creatine and electrolytes. After this they will be asked to empty their bladder. Immediately after emptying the bladder, bioimpedence will be measured. Females will be administered a urine pregnancy test. A urinalysis dipstick for protein/blood/glucose and i-STAT measurement for creatinine and electrolytes will be completed to confirm eligibility. Next, the subject will be asked to rest for 5 mins, after which baseline vitals will be taken, including blood pressure, heart rate, weight. For Visit 2 and Visit 3, the participant will be asked to review medical history and any change in status may warrant an additional baseline creatinine and blood/protein test to confirm eligibility. All studies will be repeated in the same subject using either Buoy (intervention) or water (control) or Nuun (intervention). Urine will be collected at four specific timepoints during the intervention and the volume will be recorded. If participants need to urinate between scheduled collection times, urine will be collected, volume recorded, and combined with the urine collection of the following timepoint. These urine samples will be measured and a fraction of it will be sent to the lab to be tested for the following electrolytes: sodium, potassium, chloride and urine osmolarity. Urine creatinine will also be tested at these timepoints. Additional food or beverage will not be allowed throughout the study period.

VISIT 1---BUOY INTERVENTION: The goal is to give 600mg of Na+ over 4 hours while measuring urine output over 6 hours. The recommended Buoy dosage is ¹/₃ tsp in 237 ml of water (50mg Na+) multiple times a day (Table 1). Therefore, to safely achieve a total dose 600mg Na+ (6-fold increase from single dose) we will use 4 tsps (18 ml) of Buoy diluted in 1 L of water.

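### All participants take Buoy first, water second and Nuun third, so the beverage effect cannot be separated from a visit-order effect

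*Combined protocol and SAP*

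**What the plan says.** Study Design, item 2 labels the trial as follows: "The proposed study will be conducted as a single-center prospective, cross-over, placebo-controlled clinical trial". Research Activities, item 1 then fixes one beverage to each numbered visit:

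- "VISIT 1---BUOY INTERVENTION: The goal is to give 600mg of Na+ over 4 hours"
- "VISIT 2—WATER CONTROL: Participants will ingest 1 L of water"
- "VISIT 3—NUUN INTERVENTION: The goal is to give a one-time dose of 2 tablets of Nuun Sport"

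The visit numbers run in time order. The same item states: "For Visit 2 and Visit 3, the participant will be asked to review medical history and any change in status", which makes sense only if Visit 1 has already taken place. The Consent Process section likewise places eConsent ahead of screening and Visit 1.

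On spacing, Study Design, item 4 says only this: "Study visits will be completed within a three-to-four month period". No interval between visits is given.

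The analysis (Study Design, item 8) is a condition by time ANOVA, with a one-way ANOVA for the beverage hydration index and Tukey or contrast testing as appropriate, at 0.05. It names no period or sequence term. The available text does not mention randomisation, counterbalancing or washout for this trial. The only use of the word is in the title of a cited reference.

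**The concern.** A cross-over removes between-person variation, but it protects against changes over time only if the order of conditions varies between people. Here it does not. Anything that differs between a person's first, second and third visit is added in full to the beverage comparison.

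The plan itself gives reasons to expect such differences. Visits may be spread over three to four months. It records menstrual dates because ovulation affects water retention, but it does not schedule visits by cycle. It asks for a food fast and allows one 8 oz drink, but otherwise leaves pre-visit water intake unstandardised, so habits may change as participants learn the procedure. Familiarity with the visit, season and training may also shift.

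All three aims compare beverages, and Aim 3 (Buoy against Nuun) compares the two visits furthest apart. A significant Buoy-water difference could be no more than a Visit 1 against Visit 2 difference. Because the study is meant to inform a larger trial, a biased estimate would carry forward. Loss to follow-up is tied to beverage as well: a participant who leaves after a completed visit lacks Nuun, or water and Nuun, but never Buoy.

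**Working it through.** The plan gives no power or effect-size figure, so there is nothing of its own to reproduce. The check has three parts.

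**Inputs.** From the plan: 30 completers, 34 enrolled, three beverages at three visits, significance level 0.05. Assumed: a two-sided test, and the size of any visit shift.

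**1. Can beverage be separated from visit?** Write the outcome as subject effect + visit effect π + beverage effect τ + error. Under the fixed order:

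mean(Buoy) − mean(water) = (τ_Buoy − τ_water) + (π₁ − π₂)

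mean(Buoy) − mean(Nuun) = (τ_Buoy − τ_Nuun) + (π₁ − π₃)

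Only these sums can be estimated. The design matrix shows the same thing:

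| Design | Columns | Rank | Beverage df after visit |
|---|---|---|---|
| Fixed order, n = 30 | 30 + 2 + 2 = 34 | 32 | 0 |
| Fixed order, n = 34 | 34 + 2 + 2 = 38 | 36 | 0 |
| Three-order Latin square, n = 30 | 34 | 34 | 2 |
| All six orders, n = 30 | 34 | 34 | 2 |

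The time factor in the planned ANOVA is most naturally the urine collections at 60, 120, 240 and 360 minutes within a visit. It does not adjust for visit order.

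**2. How large could the consequence be?** Set the true beverage effect to zero and let d be the Visit 1 to Visit 2 shift in SDs of the paired difference. A paired t-test has 29 df, critical value 2.045 and non-centrality d√30. For d = 0.25 this is 0.25 × 5.477 = 1.369. Tukey's adjustment for three conditions has critical t of about 2.41 on 58 df, assuming sphericity, with the same non-centrality.

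| Assumed shift d | d√30 | Paired test, P(reject) | Tukey, P(reject) |
|---|---|---|---|
| 0 | 0 | 5.0% | 1.9% |
| 0.10 | 0.548 | 8.3% | 3.8% |
| 0.25 | 1.369 | 26.3% | 15.9% |
| 0.40 | 2.191 | 56.3% | 42.1% |
| 0.50 | 2.739 | 75.4% | 63.1% |

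For the overall repeated-measures F test (4,000 simulated trials, n = 30), a linear drift from Visit 1 to Visit 3 of 0.25, 0.5, 0.75 or 1.0 within-subject SD gives rejection rates of about 13%, 37%, 72% and 93%, against a nominal 5%.

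**3. What does a balanced order do?** With 30 completers over six orders (30/6 = 5 each), every beverage falls in every visit position 30/3 = 10 times. Each beverage mean then contains (π₁ + π₂ + π₃)/3, which cancels from every contrast. The variance of a contrast is unchanged at 2σ²/30 = 0.0667σ². Residual df go from 90 − 32 = 58 to 90 − 34 = 56. With a period term, the simulated false-positive rate stays between 4.5% and 5.5% for drifts of 0 to 1 within-subject SD.

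**The case against.** The strongest reply has five parts.

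- **Inference.** The plan never states that it is non-randomised, and the data sheet and consent form are not shown. This is true, but nothing suggests that the visit numbers are mere labels, and the status check at Visits 2 and 3 points the other way. If the order was in fact randomised, the protocol must say so.
- **No demonstrated drift.** The plan standardises arrival time, overnight fasting, exercise, alcohol, morning coffee and bladder emptying. The mechanisms named are plausible rather than quantified. Buoy and water are at adjacent visits, and enrolment over about nine months means participants need not share one seasonal shift. All of this stands as a limit on the likely size of any shift. It does not touch the aliasing, and under this design a shift could be neither detected nor ruled out.
- **Attrition.** In a complete-case paired analysis, a participant who leaves is absent from every condition, so the pattern of missing beverages does not by itself bias the contrast. It matters if incomplete participants are analysed, which the plan does not settle. Attrition is therefore a secondary point.
- **The test used.** The plan allows Tukey testing, which lowers the rates as tabulated. They remain far above Tukey's own 1.9% at shifts of 0.25 and more.
- **Pilot status.** This explains the absent power calculation. It does not remove confounding from a study that tests at 0.05 and is meant to inform a larger one.

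**Conclusion.** The concern holds. As the plan is written, beverage and visit order are completely aliased: beverage has 0 df after visit at 30 or 34 participants. None of Aims 1 to 3 can be answered free of visit-order effects. This rests only on the fixed assignment of beverage to visit and on the absence of any text on order in the available document.

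The size of the resulting bias is unknown. The false-positive rates of 8% to 75% are for an unadjusted paired test with assumed shifts of 0.10 to 0.50 SD. They illustrate what an undetected shift would do and are not evidence that one exists. This must be fixed before the beverage comparisons can be interpreted.

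**What to change.** Randomise each participant to one of the six orders of the three beverages: five completers per order at 30, or five to six per order at 34 enrolled. A three-order Latin square would also separate beverage from visit, but six orders also balance which beverage precedes which. The list can be held in the REDCap system already used for eConsent. Replace the Visit 1, 2 and 3 headings with beverage names and state that order follows the randomisation list. Fit period as a fixed effect in every model. Specify one common minimum interval between visits. Balancing removes bias from additive visit effects; unequal carry-over is a separate matter, which the interval partly addresses.

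For visits not yet run, the cost is a protocol amendment, a randomisation list, a consent wording change and two residual degrees of freedom, with no extra participants, visits or tests. Enrolment status is not given, but the listed consent form is dated 2/5/2024 and primary analyses were due 4/1/2024. Data already collected in the fixed order cannot be repaired by re-ordering. Any report of them should state that beverage and visit order are inseparable and should not feed the contrasts into the future trial as unbiased estimates.

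Randomising order will not separate product from drinking schedule in Aim 3, which compares divided Buoy with bolus Nuun.

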Related to the above, it is well-accepted that electrolyte replenishment is of importance both during and following exercise, to aid in rehydration for subsequent exercise bouts [6,11]. Electrolytes (sodium in particular) have been used for decades to aid athlete hydration, and this has led to the development of various sport drinks —which also often include moderate amounts of carbohydrate (e.g., Gatorade® (PepsiCo; Chicago, IL, USA) and Powerade® (The Coca-cola Company; Austin, TX, USA)). However, one problem with carbohydrate ingestion is that some individuals experience gastrointestinal (GI) upset following carbohydrate ingestion before [12] and during an event [13], despite very good physical performance outcomes. Due to this GI upset, some individuals (in particular, recreationally active individuals who are not competing at high levels) rely solely on water and seek a method to ingest the lost electrolytes. In addition, some individuals prefer to have both plain water and an electrolyte beverage during their training/competition sessions, and in some activities (e.g., running and cycling), carrying multiple bottles of fluid is difficult.

Buoy is an all-natural, organic, FDA compliant dietary electrolyte supplement that can be dissolved in 8-12oz water (or other liquid) and provide electrolytes in servings of 1/3 teaspoon. This study will evaluate Buoy in hydrating active adults.

1. Perrier E.T. Shifting Focus: From Hydration for Performance to Hydration for Health. Ann. Nutr. Metab. 2017;70:4–12. doi: 10.1159/000462996. [PubMed] [CrossRef] [Google Scholar]

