- 1. * Select a Storage Type: UPMC owned desktop, laptop or other device
- 2. Description:
- 3. * Will identifiable data be stored in this location?
 Yes No
- 4. * Will sensitive data be stored in this location?
 Yes No
- 5. Will de-Identified or anonymous data be stored in this location?
 Yes No
- 6. * Is anti-virus software installed and up to date on all devices and are the operating systems kept up-to-date on all devices?
 Yes O No
- 7. Provide additional information as needed:

1. * Research Activity: Blood draw

2. Common Risks:

Hematoma, bruising

3. Infrequent Risks:

Fainting

1. * Research Activity: Nuun

2. Common Risks:

3. Infrequent Risks:

Nausea, dislike of taste

1. * Research Activity:

Ingestion of water

2. Common Risks:

3. Infrequent Risks:

Water intoxication can occur if consuming 4-5 L of water in a few hours, symptoms include headache, cramping weakness, nausea, vomiting, drowsiness and fatigue.

1. * Research Activity: Buoy

2. Common Risks:

3. Infrequent Risks:

Nausea, dislike of taste

1. * Research Activity:

Collection and storage of private health information

2. Common Risks:

3. Infrequent Risks:

Risk of breach of confidentiality

1. * Research Activity:

Fasting

2. Common Risks:

Headache, dizziness, hunger

3. Infrequent Risks:

Fainting

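### The Buoy dose of 600 mg sodium is 12 single doses, not 6; and 4 tsp equals 18 ml only if a serving is 1.5 ml

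*Combined protocol and SAP*

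**What the plan says.** The dosing is set out in Research Activities, item 1, under Visit 1 (Buoy intervention). The target is explicit: "The goal is to give 600mg of Na+ over 4 hours while measuring urine output over 6 hours". The recommended Buoy serving is one third of a "tsp in 237 ml of water (50mg Na+) multiple times a day (Table 1"). From this the plan derives the study dose: "safely achieve a total dose 600mg Na+ (6-fold increase from single dose) we will use 4 tsps (18 ml) of Buoy". That amount goes into one litre of water.

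The serving size is given in the same terms in the background (Study Aims, item 2), where Buoy "can be dissolved in 8-12oz water (or other liquid) and provide electrolytes in servings of 1/3 teaspoon", and again later in Research Activities.

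For Visit 3 the comparator is matched on nominal sodium: "The goal is to give a one-time dose of 2 tablets of Nuun Sport (600mg Na+) at the start of the trial".

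The form's instruction at the head of the item reads: "This description of activities should be complete and of sufficient detail to permit an assessment of associated risks". The Buoy entry under Risk and Benefits lists only "Nausea, dislike of taste" and gives no dose.

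**The concern.** Two statements in the dosing sentence do not fit the figures around them.

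The first is the multiple. A single dose of 50 mg and a total of 600 mg do not differ by a factor of six. The multiple sits in the clause that presents the dose as safe, in a section meant to support a risk assessment, so it should be right.

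The second is the volume. The sentence treats 4 tsp and 18 ml as the same amount, which implies a 4.5 ml teaspoon. If the teaspoon is a standard one, the two measures are different amounts of product and cannot both carry 600 mg of sodium. The sodium dose is the intervention, it is nominally matched to the Nuun visit, and urine volume and electrolytes are endpoints. The amount given should therefore be unambiguous.

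**Working it through.** **Inputs from the documents** (Research Activities, item 1): single dose 1/3 tsp = 50 mg Na+ in 237 ml; total dose 600 mg Na+ over 4 hours; amount of product 4 tsp, also given as 18 ml; diluent 1 L; Nuun dose 600 mg Na+.

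**Input assumed:** the documents give no ml per teaspoon. The range used is 4.93 ml (US customary) to 5.0 ml (metric).

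**1. Trying to reproduce the stated 6-fold**
- Total over single dose: 600/50 = 12.
- Increase over single dose: (600 − 50)/50 = 11.
- Concentration against the 237 ml serving: 50/0.237 = 211 mg/L, and 600/211 = 2.84.
- Concentration against a 12 oz serving (1.5 × 237 = 355.5 ml): 50/0.3555 = 141 mg/L, and 600/141 = about 4.3.
- Rate: 600 mg / 4 h = 150 mg/h = 3 servings per hour.

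None gives 6. Six single doses would be 6 × 50 = 300 mg, or 2 tsp.

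**2. Independent check from the amount of product**
- Servings: 4 tsp / (1/3 tsp) = 12.
- Sodium: 12 × 50 = 600 mg.

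The 50 mg, 600 mg and 4 tsp figures agree on 12. Only the 6 disagrees.

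**3. Volume, conditional on the assumed teaspoon**
- Implied by the plan: 18/4 = 4.5 ml per teaspoon, or 18/12 = 1.5 ml per serving.
- Four standard teaspoons: 4 × 4.93 = 19.7 ml; 4 × 5.0 = 20.0 ml.

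| Sodium content taken as right | If 4 standard tsp are measured | If 18 ml is measured |
|---|---|---|
| 50 mg per standard 1/3 tsp | 600 mg | 540 to 548 mg (9 to 10% low) |
| 50 mg per 1.5 ml | 657 to 667 mg (about 10 to 11% high) | 600 mg |

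For the upper right cell: 18/5.0 = 3.60 tsp = 10.8 servings = 540 mg; 18/4.93 = 3.65 tsp = 10.95 servings = 548 mg. For the lower left cell: 600 × 19.72/18 = 657 mg; 600 × 20.0/18 = 667 mg.

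The delivered dose is therefore on target if staff use the measure that matches the product's true sodium content, and about a tenth off if they use the other.

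**The case against.** The case for leaving the sentence alone has three parts.

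First, a reader has every number needed to see 12. The 50 mg serving is in the sentence before, and 600 mg and 4 tsp are in the same sentence as the multiple. Risk assessment rests on the absolute sodium, which is stated plainly and equals the Nuun dose. This stands, and it limits the severity.

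Second, the multiple is inert. The target, the amount of product, the dilution and the drinking schedule do not depend on it, and neither does any endpoint or analysis. This also stands. It makes the correction editorial but does not make the figure right.

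Third, the volume mismatch is not proved by the documents. The teaspoon is undefined, the serving content is referred to a Table 1 that is not in the available text, and 18 ml is exactly 12 servings of 1.5 ml. This stands too: the volume point is a conditional query, not a demonstrated error. What survives is that at a standard teaspoon 4 tsp and 18 ml are different amounts, and the plan does not say which one staff measure.

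Two stronger readings are tempting. A reader might infer that the 6 is right and the 50 mg wrong, so that a serving holds 100 mg and 4 tsp holds 1,200 mg. No text gives a 100 mg serving, and the agreement of 50 mg, 600 mg and 4 tsp points the other way. A reader might also infer that the safety assessment was misled, since the Buoy risk entry carries no dose. The documents do not show that anyone relied on the multiple; the absolute dose is disclosed, and the product is described as taken several times a day.

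**Conclusion.** The multiple is wrong on the documents' own figures. 600 mg is 12 single doses of 50 mg, so 6-fold understates it by half. This part needs no outside assumption.

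The volume discrepancy holds only if the teaspoon is 4.93 to 5.0 ml. On that assumption, and with 50 mg per 1/3 tsp, measuring 18 ml would give about 52 to 60 mg less sodium than the 600 mg intended for both the Buoy and Nuun visits. If a serving is 1.5 ml, 18 ml is correct and it is the teaspoon count that fails as a standard measure.

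Overall this is a minor point. No safety harm follows, and the effect on conclusions is likely small: Buoy is a large sodium load relative to water either way, and the Buoy and Nuun visits already differ in product and in drinking time (4 hours against 30 minutes).

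**What to change.** In the Visit 1 text, replace 6-fold with 12-fold, or say that the total equals 12 single doses of 50 mg.

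Check sodium per ml against the product label or Table 1. Then prescribe one quantity in ml and state the sodium it delivers: about 20 ml if 50 mg per standard 1/3 tsp is confirmed, or 18 ml if the label serving is 1.5 ml. Drop the teaspoon figure, or keep it only as a count of label servings. If any Buoy visits have already taken place, record which measure was used and report the sodium actually given.

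The cost is one label check and one corrected sentence. The design, visits and analysis are unchanged.
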